- 7) Measures of functioning: Quality of Life (QoL) at Weeks 1 and 12 and Treatment Effectiveness Assessments (TEA) at Week 12;
- 8) Measures of adverse events during Weeks 1-12: number and severity of adverse events reported; number and outcomes (fatal, non-fatal) of overdose events reported;
- 9) Self-reported measures of alcohol, tobacco and other drug use during Weeks 1-12 (TLFB) and UDS results of other substance use not quantified for primary or secondary outcomes;
- 10) Urinalysis results indicating a new chlamydia or gonorrhea diagnosis at Week 12;
- 11) Iowa Gambling Task (IGT) performance at screening.

Study Population	The study will consist of approximately 246 males and females who meet eligibility criteria, including Diagnostic and Statistical Manual of Mental Disorders-5 (DSM-5) criteria for moderate to severe MUD and co-occurring mild OUD or opioid misuse not warranting MOUD, supported by urine samples positive for MA and negative for opioids during screening.
Phase or Stage	This is a Phase IIb double-blind, randomized, placebo-controlled trial.
Description of Sites Enrolling Participants	The trial will include 4-8 sites with appropriate staffing and facilities to conduct all study procedures and will not include sites outside of the United States.
Description of Study Intervention	The study intervention is 3 doses of 300mg BUP-Inj delivered by abdominal subcutaneous injection every 4 weeks.
Safety Reporting	Appropriately qualified and trained personnel will elicit participant reporting of Adverse Events (AEs) and Serious Adverse Events (SAEs) at each study visit. Study personnel will obtain as much information as possible about the reported AE/SAE to complete the AE/SAE forms and will consult with the Safety Monitor/Medical Monitor as warranted. Standard reporting, within seven days of the study site becoming aware of the event, will be required for reportable AEs. Expedited reporting, within 24 hours of the site's becoming aware of the event, will be required for reportable SAEs (including death and life-threatening events).
Analyses	Primary Statistical Analysis: Generalized estimating equations will be used to model the log-odds of a MA-negative UDS during Weeks 9-12, assuming an autoregressive lag-1 working correlation matrix. The robust (sandwich) estimator will be used to adjust the covariances for the correlation of UDS from the same participant. Missing UDS are imputed as MA-positive.

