5.3 Exploratory Objective(s)

Data will be collected to explore whether assignment to BUP-Inj compared to PBO-Inj over the 12 week medication phase corresponds with:

1. Measures of subjective effects of MA:
 - a. MA withdrawal, as measured by scores on the Amphetamine Cessation Symptom Assessment during Weeks 1-12
 - b. MA craving as measured by the Visual Analog Craving Scales (VAS) during Weeks 1-12
2. Measures of opioid subjective effects:
 - a. Observer rating of opioid withdrawal as measured by the Clinical Opiate Withdrawal Scale (COWS) on the day of randomization; each subsequent visit during induction in Week 1, if needed; prior to each injection in Weeks 1, 5, and 9, and at Week 12.
 - b. Self-reported rating of opioid withdrawal as measured by the Subjective Opiate Withdrawal Scale (SOWS) on the day of randomization; each subsequent visit during induction in Week 1, if needed; prior to each injection in Weeks 1, 5, and 9, and at Week 12.

- c. Self-reported opioid craving, as measured by Visual Analog Craving Scales (VAS), Weeks 1-12
 3. Self-reported craving for MA and opioid co-use, as measured by Visual Analog Craving Scales (VAS), Weeks 1-12
4. Measures of mood, pain, and stress:
 - a. Self-reported depressive symptoms as measured by the Inventory of Depressive Symptomology - Self-Report (IDS-SR) during Weeks 1-12
 - b. Change in self-reported anxiety symptoms as measured by the Generalized Anxiety Disorder Scale-7 (GAD-7) during Weeks 1-12
 - c. Changes in self-reported mood symptoms as measured by the Concise Associated Symptom Tracking Scale (CAST) during Weeks 1-12
 - d. Changes in self-reported anhedonia as measured by the Dimensional Anhedonia Rating Scale (DARS) during Weeks 1, 5, 9, and 12
 - e. Changes in reported pain as measured by the Pain Frequency, Intensity, and Burden Scale (P-FIBS) during Weeks 1-12
 - f. Changes in self-reported stress as measured by the Perceived Stress Scale (PSS) during Weeks 1, 5, 9, and 12
5. Retention:
 - a. Participants retained in treatment (defined as present and providing urine drug samples) during Weeks 1-12
6. Measures of infectious disease control, incidence, and risk:
 - a. Biomarkers measured at Week 12:
 - i. HIV-Negative Participants: Remaining HIV-negative
 - ii. HCV-Negative Participants: Remaining HCV-negative
 - b. Self-Reported HIV transmission risk behaviors measured at Weeks 1, 6 and 12:
 - i. Self-reported number of new sexual partners

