 - ii. Self-reported number of sexual partners with condomless sex who are serodiscordant or unknown serostatus
 - iii. Self-reported number of sexual partners with condomless sex who are serodiscordant or unknown serostatus with whom substances were used during sex (chemsex)
 - iv. For men, self-reported number of male sexual partners
 - v. Self-reported number of episodes sharing needles
 - vi. Self-reported number of episodes sharing injection equipment and paraphernalia
7. Measures of functioning:
 - a. Self-reported assessment of Quality of Life (QoL) at Weeks 1 and 12
 - b. Self-reported overall functioning as measured by the Treatment Effectiveness Assessment (TEA) at Week 12

RESTRICTED

8. Measures of adverse events:
 - a. Number and severity of adverse events reported during Weeks 1-12
 - b. Number and outcomes (non-fatal, fatal) of overdose events during Weeks 1-12
9. Changes in other substance use measured by self-report (TLFB) and UDS. Alcohol, tobacco, and other drugs measured via self-report will be collated and counted, and UDS results will quantify the presence of barbiturates, benzodiazepines, cocaine, amphetamines, marijuana (THC), methadone, phencyclidine (PCP) and ecstasy (MDMA).
10. Changes in disease transmission, with new chlamydia or gonorrhea diagnoses measured via urinalysis.
11. Participants will complete the Iowa Gambling Task (IGT) at screening to determine if performance on the IGT predicts treatment response. The IGT is a standard computer-based task with established performance in people receiving treatment for MUD ⁴⁴.

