 - a. Changes in self-reported assessment of Quality of Life (QoL) at Week 1 and 12
 - b. Self-reported overall functioning as measured by the Treatment Effectiveness Assessment (TEA) at Week 12

RESTRICTED

8. Measures of adverse events:
 - a. Number and severity of adverse events reported during Weeks 1-12
 - b. Number and outcomes (non-fatal, fatal) of overdose events during Weeks 1-12
9. Self-reported measures of alcohol, tobacco and other drug use on TLFB at Weeks 1, 5, 9, and 12, and UDS results of other substance use not quantified for primary or secondary outcomes.
10. Urinalysis results indicating a new chlamydia or gonorrhea diagnosis at Week 12
11. IGT performance at screening

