Cognitive Behavioral Therapy Documentation			X	X	X	X	X	X	X	X	X	X	X	X	X	X
Iowa Gambling Task and Documentation		X*														
Treatment Effectiveness Assessment																X ²
Cannabis Use Assessment			X													
Tobacco Use History (PhenX Tier 1)			X													X ²
Quality of Life (PhenX Tier 1)			X													X ²
Semi-Structured Qualitative Interview			X ^E													
Adherence Measures																
Buprenorphine-XR/Placebo Injection				X ²				X				X				
BUP-SL Dispensing				X ¹												
Laboratory Evaluations																
Urine Screening for Disease			X*												X	
Complete Blood Count			X*												X	
Blood Chemistry			X*													
Liver Function Tests			X*												X	
Disease Serology			X*												X	
Blood Sample for UTSW Repository			X*												X	
Blood Sample for NIDA Genetic Testing and Family Origin								X ^C								

Study Phase	Prescreening	Screening	Medication Phase												Follow-up
			1	2	3	4	5	6	7	8	9	10	11	12	
Study Week		-21 to -1	1	2	3	4	5	6	7	8	9	10	11	12	16
Buprenorphine Blood Levels							X ^A				X ^A			X	
Administrative and Other Forms															
Locator Form		X*			X		X			X			X		
Eligibility - Randomization (Enrollment Form)			X												
Visit Documentation Form		X+	2X	2X	2X	2X	2X	2X	2X	2X	2X	2X	2X	2X	X
Mental Health Follow-Up Assessment ^B															
End of Medication Form														X ²	
Protocol Deviation and Review ^B															
Treatment Satisfaction															X
Study Completion															X

NOTES:

X* = once during screening

X+ = at each screening visit

X^A = at each induction visit, including if additional induction visits are required during the medication phase, and on the day of first injection

X = a procedure or assessment performed once per week and preferably at the first visit of the week, unless otherwise noted

2X = a procedure or assessment performed twice per week

X¹ = on the day of induction only

X² = collected at the second visit of the week

^A Must be collected prior to administration of any medications at the visit

^B Completed as applicable

^C If consent is provided, collect sample on day of 2nd injection if possible. Otherwise, to be collected at any future visit with blood draw.

^D Collected at screening visit(s) with a UDS negative for opioids and on the day of expected randomization

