11.4.2 Timeline Followback (TLFB)

The Timeline Followback procedure⁵⁰ will be used to elicit the participant's self-reported use of substances, including MA, opioids, and MA/opioid co-use during the screening phase and throughout study participation. During the screening phase, this form will be used to assess substance use for the 30-day period prior to written consent. During the trial, TLFB will be administered to document the participant's self-reported use of substances for each day since the previous TLFB assessment. For participants who report opioid use or who have a positive urine drug screen for opioids during the trial, Medical Clinicians will offer them the opportunity to withdraw from the medication aspects of the trial and to initiate MOUD through a referral to appropriate care. In the event that participants decline this offer, this will be recorded in the participant's study record.

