number of male sexual partners, (f) Self-reported number of episodes sharing needles, and (g) Self-reported number of episodes sharing injection equipment and paraphernalia will each be analyzed using a repeated measures mixed effects model for count data outcomes. If zero-inflation is observed a zero-inflated poisson, negative binomial, or hurdle model will be used depending on which model best fits the data. However, if an outcome has low counts, we may collapse it into a binary (presence/absence) outcome. If the data are very sparse, we may collapse across weeks and use a logistic regression model.

7. *Measures of functioning:*

- a. Changes in self-reported assessment of Quality of Life (QoL) at Week 1 and Week 12 will be analyzed using repeated-measures mixed-effects model, with terms for time, treatment group, treatment group by time interaction, baseline measure of the outcome, and any covariates. Person effects will be random and all other effects fixed.
- b. Self-reported overall functioning as measured by the Treatment Effectiveness Assessment (TEA) at Week 12 will be analyzed using analysis of covariance.
8. *Measures of adverse events:* both (a) Number and severity of adverse events reported during Weeks 1-12 and (b) Number and outcomes (non-fatal, fatal) of overdose events during Weeks 1-12 will be analyzed using Chi-square tests for each measure of AEs.
9. Self-reported measures of alcohol, tobacco and other drug use on TLFB at Weeks 1, 5, 9, and 12, and UDS results of other substance use not quantified for primary or secondary outcomes will be analyzed using a repeated-measures mixed-effects model for continuous outcome (amount of use) or binary outcome (presence/absence of use). The models will have terms for time, treatment group, treatment group by time interaction, baseline measure of the outcome, and any covariates. Person effects will be random and all other effects fixed.
10. Urinalysis results indicating a new chlamydia or gonorrhea diagnosis at Week 12 will be analyzed using a logistic regression with the presence of a Week 12 diagnosis as the outcome and treatment group and other covariates and predictors.
11. IGT at screening as a predictor of treatment response will be analyzed using the primary outcome analysis being repeated with the addition of terms for baseline IGT performance and IGT by time interaction.

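### Other-substance use on the Timeline Followback is analysed only at Weeks 1, 5, 9 and 12, although the synopsis defines it over Weeks 1-12 and every day is recorded.

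*Combined protocol and SAP*

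**What the plan says.** The current text defines the measure in two ways.

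- **Synopsis (Section 2.1), exploratory measure 9:** "Self-reported measures of alcohol, tobacco and other drug use during Weeks 1-12 (TLFB"), that is, the full medication phase.
- **Section 7.3, item 9:** "Self-reported measures of alcohol, tobacco and other drug use on TLFB at Weeks 1, 5, 9, and 12, and UDS results" for substances not counted in the primary or secondary outcomes.
- **Section 16.6, item 9:** "Self-reported measures of alcohol, tobacco and other drug use on TLFB at Weeks 1, 5, 9, and 12", the same four weeks, analysed by a repeated-measures mixed-effects model for amount or presence of use. The terms are time, treatment, their interaction, a baseline measure and covariates.

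Section 5.3 does not settle it. Its lead-in asks whether assignment "over the 12 week medication phase corresponds with" the listed measures, and its item 9, "Changes in other substance use measured by self-report (TLFB) and UDS", names no weeks.

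On data collection, Table 11.1 marks the TLFB row 2X in each of Weeks 1 to 12, and its key reads "2X = a procedure or assessment performed twice per week". Section 11.4.2 says the form covers "self-reported use of substances for each day since the previous TLFB assessment". The methamphetamine, opioid and co-use TLFB outcomes in Section 7.2 all use Weeks 1-12, with a range of 0-84.

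**The concern.** One measure has two definitions, and the narrower one stands in the analysis section. It uses a third of a diary that is collected daily, while the other outcomes taken from the same form use all of it. Weeks 1, 5, 9 and 12 are also the weeks at which the anhedonia and stress scales are scheduled. That pattern suits instruments given only at those visits; it does not suit a diary kept up twice a week. The list may have been carried over from those scales, but that is inference.

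Two things are at stake. The first is some precision, together with any change in use that falls wholly in Weeks 2-4, 6-8 or 10-11. The second is that conflicting definitions leave the choice of analysis weeks open until after the data are seen.

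**Working it through.** **Inputs**
- Weeks named for the TLFB part of item 9: 4 (Sections 7.3 and 16.6).
- Weeks in the synopsis definition: 12.
- TLFB administrations: 2 per week (Table 11.1).
- Look-back: to the previous TLFB, with daily records (Section 11.4.2).
- Maximum TLFB days over Weeks 1-12: 84 (Section 7.2, stated for methamphetamine, opioid and co-use days).

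**Step 1. Reproduce the plan's figure.** 12 weeks × 7 days = 84 days, as Section 7.2 states. Administrations: 12 × 2 = 24.

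**Step 2. Count what the four weeks hold.** 4 × 7 = 28 days, and 28/84 = 33%. Administrations: 4 × 2 = 8 of 24. Left out: 84 − 28 = 56 days, and 56/84 = 67%.

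**Step 3. Can the named weeks recover the others?** No. Each form reaches back only to the previous form, about 3-4 days on a twice-weekly schedule. Forms completed in Week 5 do not cover Weeks 2-4.

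**Step 4. Precision.** The documents give no within-person correlation, so equal correlation r between weeks is assumed and a range is shown. In units of the variance of one week's value, the variance of a participant's mean over k weeks is

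V(k) = (1 + (k − 1)r) / k.

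| r (assumed) | V(4) | V(12) | Cut in variance, 1 − V(12)/V(4) |
|---|---|---|---|
| 0.3 | 1.9/4 = 0.475 | 4.3/12 = 0.358 | about 25% |
| 0.5 | 2.5/4 = 0.625 | 6.5/12 = 0.542 | about 13% |
| 0.7 | 3.1/4 = 0.775 | 8.7/12 = 0.725 | about 6% |

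The matching cuts in standard error, 1 − √(V(12)/V(4)), are about 13%, 7% and 3%.

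This describes a participant's average over the phase. It does not give the precision of a contrast at one week, and a correlation that fades with time would give other figures.

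**The case against.** The strongest reply has four parts.

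1. **The analysis window is not defined.** The plan does not say which days a value at Week 5 summarises. If it meant all days since the previous named week, little would be lost. This stands to the extent that the count of 56 days is conditional on the calendar-week reading. Nothing in the plan states the longer window, though, and the look-back in Section 11.4.2 is short.
2. **A formal SAP is still to come (Section 16.0).** It could specify the window, but its author would still have to choose between two protocol definitions.
3. **Safety does not hang on this model.** A reader might infer that the four-week list hides changes in sedative use. The documents do not support that. The list attaches only to the TLFB part of item 9. The urine screen is done twice weekly in Weeks 1-12 and includes benzodiazepines and barbiturates (Section 11.4.1). Appendix B has substance use recorded and monitored at every visit, and adverse events and overdoses are analysed over Weeks 1-12 under item 8. This part stands in full.
4. **It is one exploratory item among eleven.** This also stands.

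A reader might also infer that Week 1 is mostly before the first injection and should be dropped. Section 6.1.1 starts Week 1 at Day 0, and Section 6.1.2 expects the injection about Day 3. In calendar days, then, Days 0-2 (3 of 7) precede it and Days 3-6 (4 of 7) do not. Analysing only post-injection weeks would also depart from the synopsis and from the Section 7.2 TLFB outcomes.

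**Conclusion.** The inconsistency is real and unexplained. Sections 7.3 and 16.6 name four weeks, the synopsis names twelve, and daily data exist for all twelve. The day count assumes that each named week means its seven calendar days. The precision gain is modest and rests on assumed, equal correlations. The comparison that matches the documents is 4 weeks against 12; setting 3 against 11 by dropping Week 1 would give larger cuts (32%, 18% and 9%) for a contrast that the plan does not contain.

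The effect falls mainly on alcohol, tobacco and drugs not on the urine panel. The primary analysis, sample size, alpha and visit-level safety monitoring do not change. This is a worthwhile tidy-up and not a threat to the trial.

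**What to change.** - In Section 7.3 item 9 and Section 16.6 item 9, replace the list of four weeks with Weeks 1-12, to match the synopsis.
- State the unit of analysis: a weekly TLFB summary (amount or presence of use) for each of the 12 weeks, fitted with the mixed-effects model already planned.
- Name the 30-day pre-consent TLFB as the baseline term. Section 11.4.2 already collects it, and Section 16.3.2 uses it as the baseline for methamphetamine days.
- If four weeks are intended after all, give the reason, define the days that each time point covers, and change the synopsis to agree.

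The cost is an edit to two items and a short definition of the weekly summary. No extra visits, forms or participants are needed.

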2.0 PROTOCOL SUMMARY

2.1 Synopsis

Title	Randomized, double-blind, placebo-controlled trial of monthly injectable buprenorphine (BUP) for methamphetamine (MA) use disorder (MURB)
Study Number	CTN-0110
IND Number	161851
Study Description	This study is a 12-week randomized, double-blind, placebo-controlled trial that will investigate the use of injectable buprenorphine (BUP-Inj) compared to injectable placebo (PBO-Inj) for the treatment of methamphetamine use disorder (MUD) among individuals with mild co-use of opioids.
Objectives	
Primary Objective: To evaluate whether assignment to 12 weeks of outpatient BUP-Inj compared to 12 weeks of outpatient PBO-Inj reduces MA use (as measured by twice-weekly urine drug screens (UDS)) during Weeks 9-12 in participants with moderate to severe MUD with co-occurring mild opioid use disorder (OUD) or opioid misuse not warranting medication for opioid use disorder (MOUD).
 
Secondary Objectives: To evaluate whether assignment to 12 weeks of outpatient BUP-Inj compared to 12 weeks of outpatient PBO-Inj among participants with moderate to severe MUD with co-occurring mild OUD or opioid misuse not warranting MOUD improves: 1) outcomes related to alternate measures of MA use including total number of MA negative urine drug screens (UDS) and self-reported days of MA use; 2) measures of opioid use and self-reported frequency of opioid use; and 3) measures of MA and opioid co-use and self-reported days of MA and opioid co-use.
 
Exploratory Objectives: Include exploring whether assignment to BUP-Inj compared to PBO-Inj during the medication phase corresponds with changes in measures of subjective effects of MA including MA withdrawal symptoms and self-reported MA craving; measures of subjective effects of opioids including opioid withdrawal symptoms and self-reported opioid craving; measures of self-reported craving for MA and opioid co-use; measures of mood, stress and pain including self-reported symptoms of depression, anxiety, mood, anhedonia, stress, and pain; retention in the protocol; infectious disease markers, incidence, and Human Immunodeficiency Virus (HIV) transmission risk behaviors; measures of overall functioning; measures of adverse events and fatal and non-fatal overdose events; changes in other substance use or new sexually transmitted infections (STIs) and whether a neurocognitive measure of impulse inhibition predicts treatment outcomes.

RESTRICTED

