16.3 Statistical Methods for Primary and Secondary Outcomes

16.3.1 Primary Outcome

UDS will be collected twice a week during Weeks 9 through 12, or 8 assessments. For each assessment, the outcome will be 1 if the UDS is MA negative and 0 if the UDS is MA positive or missing. The probability of an MA negative UDS during Weeks 9-12 will be computed via a GEE approach postulating a binomial distribution with a logit link, an AR(1) correlation for the repeated observations of a single participant, and utilizing the robust (sandwich) estimator for the covariance of the regression betas. Despite other possible sources of variance such as random site effects, the regression coefficients will be asymptotically unbiased with consistent standard errors using this estimation strategy. The model will have a term for treatment group (BUP-Inj and PBO-Inj) as the between-subjects factor. The model will be used to compute an average probability of MA-negative UDS across Weeks 9 through 12 in each group. Letting y_{it} be an indicator of whether the UDS for participant i ($i=1, \dots, n$) at timepoint t during this evaluation period ($t=1, \dots, 8$), and z_i is an indicator of participant i being assigned to the BUP-Inj arm, the logistic model is given by

$$\text{logit } P(y_{it} = 1) = \alpha + \beta z_i.$$

The hypothesis will be tested by the statistical significance of the odds ratio using a two-sided test (i.e., $H_0: e^\beta = 1$; $H_1: e^\beta \neq 1$). An *a priori* alpha (i.e., type I error) of 0.05 will be used for this analysis.

SAS code to estimate the primary outcome follows:

```
proc genmod data = dat;
  class patid treat;
  model metneg(event = "1") = treat / dist = bin link = logit;
  repeated subject = patid / type = ar(1);
  run;
```

Where `patid` is the participant's unique identifier, `treat` is an indicator of being assigned to the BUP-Inj treatment arm, and `metneg` is an indicator of whether the UDS is negative for MA.

16.3.2 Secondary Outcomes (medication phase, Weeks 1-12):

1. *Alternate measures of methamphetamine use: both*

- a. MA Treatment Effectiveness Score (TES), as measured by number of UDS results negative for MA by condition, during Weeks 1-12 (score range 0-24) will be analyzed as count data, which typically follows a Poisson distribution.

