16.8.1 Subgroup Analyses

Per NIH policy, subgroup analyses will be implemented to assess whether sex, race and/or ethnicity are effect modifiers. For each demographic, a model will be fit including an interaction with treatment assignment and the subgroup effect will be reflected by a two-sided test of whether the interaction regression coefficient is different from zero. Additionally, the treatment effect will be presented for each category of the demographic factor from these interaction models.

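### The Iowa Gambling Task analysis can show whether IGT is prognostic, but it has no term for whether IGT modifies the BUP-Inj effect, and its IGT by time term serves no stated objective

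*Combined protocol and SAP*

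**What the plan says.** The purpose of the IGT analysis is worded in two ways.

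- Section 5.3 item 11 says the task is given at screening "to determine if performance on the IGT predicts treatment response". Section 16.6 item 11 repeats the idea of response.
- The synopsis (section 2.1) asks "whether a neurocognitive measure of impulse inhibition predicts treatment outcomes".

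Section 16.6 item 11 gives the method. The primary outcome model is fitted again "with the addition of terms for baseline IGT performance and IGT by time interaction".

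The model being repeated is in section 16.3.1: "The model will have a term for treatment group (BUP-Inj and PBO-Inj) as the between-subjects factor". The equation there has an intercept and a treatment coefficient, and the SAS model statement has treatment as its only covariate. Neither contains time.

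For sex, race and ethnicity, section 16.8.1 handles effect modification explicitly: "a model will be fit including an interaction with treatment assignment". IGT is not among the factors listed there.

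**The concern.** A baseline measure can predict response in two senses. A prognostic measure forecasts the outcome whichever arm the participant is in. A predictive measure identifies who gains more from BUP-Inj than from placebo. Section 5.3 introduces its exploratory list as a comparison of BUP-Inj with PBO-Inj, so the predictive sense is a natural reading of item 11. Testing it needs an IGT by treatment term, and none is planned.

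The interaction that is planned, IGT by time, asks whether the IGT association drifts over the eight visits of Weeks 9-12. No objective asks that.

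What is at stake is interpretation. A significant IGT coefficient could be reported as general prognosis when it arises only in the BUP-Inj arm. A modifier with opposite slopes in the two arms would mostly go unseen. Adding the interaction after unblinding would make it a post hoc choice.

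**Working it through.** **1. What each term can show.** Let z indicate BUP-Inj, g the IGT score and t the visit.

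- Primary model: logit P = α + βz.
- Item 11 model: logit P = α + βz + γg + δgt.
- BUP-Inj versus placebo log odds ratio at a given g and t: (α + β + γg + δgt) − (α + γg + δgt) = β, the same at every IGT score.
- With an added term θgz, the treatment effect becomes β + θg. The test of modification is θ = 0. Item 11 fixes θ at 0.
- IGT slope at visit t in the item 11 model: γ + δt, the same in both arms. So δ is drift and nothing else.

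Leaving out a time main effect also makes the result depend on coding. If the score is shifted by c, then δ(g − c)t = δgt − cδt, so with an uncentred score δ can absorb a general time trend. Likewise γ is the slope at t = 0. That is mid-window if visits are centred, and outside the window if they are numbered 1 to 8. Item 11 states neither coding.

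**2. Anchoring to the plan's figures.** Section 16.2 gives 0.17 and 0.07, N = 246 and 90% power. Odds ratio: (0.17/0.83)/(0.07/0.93) = 2.72, as stated. The simulation used these values (123 per arm, 8 visits). With no IGT effect, the treatment term was significant in 91% of simulated trials, close to the planned 90%.

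**3. Simulation.** There were 1,000 trials per row, two-sided 0.05, with robust standard errors. Assumptions not in the documents: standardised IGT, centred time, latent AR(1) correlation 0.9, and the IGT slopes (log odds per SD). An independence working correlation was used where the plan uses AR(1).

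| Assumed truth | Planned IGT main effect | Planned IGT by time | IGT by treatment (second model) |
|---|---|---|---|
| No IGT effect | 4.8% | 6.4% | 6.5% |
| Prognostic, 0.47 in both arms | 88.7% | 5.5% | 6.8% |
| BUP-Inj arm only, 0.6 | 77.6% | 5.6% | 52.8% |
| Opposite, −0.47 placebo and +0.47 BUP-Inj | 18.2% | 5.8% | 86.9% |

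Monte Carlo margin: 1.96 × √(0.05 × 0.95/1000) = 1.4 points near 5%, and 1.96 × √(0.25/1000) = 3.1 points near 50%.

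Rows two and three show the ambiguity: the planned main effect is usually significant in both, and the planned IGT by time term does not tell them apart. In the last row the slopes largely cancel.

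**4. How far the interaction power depends on the slope.** The opposite-slopes row implies an interaction of 0.47 + 0.47 = 0.94, nearly as large as the design treatment effect, ln 2.72 = 1.00. That is generous. A further simulation of the same design, with within-person correlation about 0.41 and a slope in the BUP-Inj arm only, gave interaction power of about 20% at slope 0.3, 44% at 0.5 and 63% at 0.7. At 0.7 the planned main effect was significant in 90% and IGT by time in 5.7%.

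**5. Why two models are needed.** Once IGT by treatment is included with reference coding, the IGT coefficient is the slope in the reference arm. In the prognostic row it was significant in 48% of trials (placebo as reference), against 89% for the main effect without that interaction. It should not be labelled the prognostic result.

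**The case against.** The strongest reply is that the plan does answer its question. The first added term is baseline IGT, adjusted for treatment, and it tests whether IGT predicts MA-negative UDS. The synopsis speaks of treatment outcomes, which is prognostic wording. Where the plan wants effect modification, in section 16.8.1, it says so. This largely stands. A reader might infer from the missing interaction that item 11 cannot say whether IGT predicts response at all. The documents do not support that: response is undefined, and the main effect serves the prognostic reading.

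A reader might also infer that any real modifier would be missed, or that chance drift would be reported as prediction. The first is too strong, because a modifier confined to the BUP-Inj arm would often produce a significant main effect. The second is speculative, because item 11 does not name IGT by time as the deciding test.

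Finally, this is the last of eleven exploratory analyses, and section 16.0 says a formal SAP will follow. That limits the weight of the point. It does not remove it: the plan never says which sense is meant, and the model as written cannot separate the two.

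**Conclusion.** The point holds in a limited form. Item 11 can show that IGT is prognostic, but it cannot show whether IGT modifies the BUP-Inj versus placebo effect. Its IGT by time term lacks a time main effect and matches no stated objective. Those conclusions follow from the model terms and need no assumed numbers.

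The size does rest on assumptions. Under the slopes tried, a modifier in the BUP-Inj arm alone would look prognostic in about 78% of trials, and one with opposite slopes would give a significant main effect in about 18%. An IGT by treatment test would detect these in 53% and 87%, falling to about 20% for a BUP-Inj-arm slope of 0.3. Realistic power for the interaction is therefore likely modest, and a null result should not be read as absence of modification. The primary result, sample size and alpha are unaffected.

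**What to change.** In section 16.6 item 11, and in the formal SAP before unblinding:

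1. Keep a model with treatment and IGT and no interaction, and take the prognostic estimate from it.
2. Fit a second model that adds IGT by treatment, in the form already used in section 16.8.1, as the test of effect modification. Report the IGT slope in each arm with a confidence interval.
3. Delete IGT by time, or add a time main effect, fix the coding of visit and score, and state what the term is for.

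Align the wording of sections 2.1 and 5.3 so that both the prognostic and the predictive question are named. The cost is a short change of wording and one more exploratory test. No new data are needed.
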